11.2 CLINICAL LABORATORY PARAMETERS

Descriptive statistics for clinical laboratory values (in SI units) and changes from the baseline values at each assessment time point (including the end of the open-label treatment period) will be presented for the following laboratory parameters:

[figure not shown]

[figure not shown]
11.3 VITAL SIGNS

[figure not shown]
Descriptive statistics for vital signs (ie, sitting radial pulse rate, sitting systolic and diastolic blood pressure (BP), body weight, and height) and changes from baseline values at each visit and at the end of the open-label treatment period will be presented. In addition, height and weight z scores will be calculated based on growth charts.

11.4 ELECTROCARDIOGRAM (ECG)

Descriptive statistics for ECG parameters (ie, ventricular heart rate, RR interval, PR interval, QRS interval, QT interval, and QTc) and changes from baseline values at each assessment time point will be presented. The QTc is calculated using both the Bazett and Fridericia corrections.

11.5 OTHER SAFETY PARAMETERS

Other safety parameters include C-SSRS and growth.

11.5.1 Suicidality Assessment

For the C-SSRS, the number and percentage of patients with any suicidal ideation or suicidal behavior will be presented by cohort, separately for the lifetime history, the open-label treatment period and the open-label down-taper period. The distribution of responses for the most severe suicidal ideation and suicidal behavior will be summarized by cohort and by lead-in treatment group, separately for the lifetime history, the open-label treatment period, and the open-label down-taper period. Supportive listings will be provided and will include the patient identification number, treatment group, visit number, lifetime history, and postbaseline values for each patient. Intensity of ideation, suicidal behavior type, and lethality of suicidal behavior will also be included in these listings. A listing of all AEs occurring in patients who have suicidal ideation or suicidal behavior will also be provided.

11.5.2 Growth Evaluation

Weight and height will be presented in raw score and standardized z-scores adjusted for gender and age, using the LMS method (Cole TJ, 1990).

Descriptive statistics for raw scores of height and weight, age-and-gender-adjusted height and weight, and changes from baseline values at each visit and at the end of the open-label treatment group will be presented.

12.0

HEALTH OUTCOME ANALYSES

Not applicable.

13.0**INTERIM ANALYSIS**

No interim analysis is planned for this study.

14.0**DETERMINATION OF SAMPLE SIZE**

This is a long-term open-label study of the safety and tolerability of vilazodone in pediatric patients with MDD. [REDACTED]

[REDACTED] approximately 250 patients are planned for enrollment in this study

15.0

COMPUTER METHODS

Statistical analyses will be performed

[REDACTED]

16.0

DATA HANDLING CONVENTIONS

16.1

VISIT TIME WINDOWS

Table 16.1–1 below presents the visits assigned for efficacy and safety analyses corresponding to the range of treatment days (window) in the open-label treatment period during which an actual visit may have occurred.

10. *Journal of the American Statistical Association*, 1980, 75, 338-342.

16.2 DERIVED EFFICACY VARIABLES

The total score at a particular visit will be calculated using (sum of nonmissing items) \times (total number of items) / (number of nonmissing items) only if the number of missing items is ≤ 2 for the CDRS-R score.

If a patient misses a postbaseline visit or if his/her postbaseline visit is outside of the visit time window, a record for the scheduled visit will be imputed using the last observed nonmissing value immediately before the missing value. If the missing value occurs at Week 2, the baseline value will be carried forward for Week 2, provided that at least 1 subsequent postbaseline assessment is available. For a composite scale such as CDRS-R total score, individual items of the rating scale will not be carried forward. Only total scores will be carried forward using the LOCF approach.

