9.1.1 Screening Period

[figure not shown]
Patients who completed lead-in study VLZ-MD-22 will have completed a down-taper period at the end of study VLZ-MD-22 and will not be required to undergo a washout period.

For de novo patients, the screening/washout period will generally be 1 week prior to Visit 2 (Baseline), but may be extended up to a total of 5 weeks to accommodate prior medication washout or repeat assessments (with prior approval of the Study Physician or designee). At the end of Visit 2 (Baseline), patients who meet the eligibility criteria will be enrolled into the study.

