9.3.1 Inclusion Criteria

To be eligible to participate in the study, patients must meet the following criteria:

Note: Inclusion criteria #2 through #5 are considered to have been met for patients who completed the lead-in study (VLZ-MD-22). For patients who completed the lead-in study (VLZ-MD-22), medical, psychiatric and medication histories from Screening (Visit 1) of the lead-in study will be used.

1. Be able to provide informed assent and their parent/guardian/LAR and caregiver must provide written informed consent before the initiation of any study-specific procedures (Section 5.3)
2. Be a male or female outpatient, 7 to 17 years of age, inclusive, at Screening (Visit 1; *de novo* patients only)
3. Meet DSM-IV-TR criteria for MDD, confirmed by K-SADS-PL, with a current depressive episode of \geq 6 weeks duration at Screening (Visit 1; *de novo* patients only)
4. Have a score of \geq 40 on the CDRS-R at Screening and Baseline (Visits 1 and 2, respectively; *de novo* patients only)
5. Have a Clinical Global Impressions–Severity (CGI-S) score \geq 4 at Screening and Baseline (Visits 1 and 2, respectively; *de novo* patients only)
6. Have a caregiver who is willing and able and provides consent to be responsible for safety monitoring of the patient, providing information about the patient's condition, overseeing the administration of investigational product, and accompanying the patient to all study visits (Section 5.3)
7. Have normal physical examination findings, vital sign values, clinical laboratory test results, and electrocardiogram (ECG) results, or abnormal results that are determined by the Investigator not to be clinically significant
8. Have a negative serum β -human chorionic gonadotropin (β -hCG) pregnancy test result if patient is female \geq 9 years of age or has had onset of menses

[figure not shown]

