**9.2****MEASUREMENT OF TREATMENT COMPLIANCE**

10.0

EFFICACY ANALYSES

All efficacy analyses will be based on the ITT Population. For patients who completed the lead-in study (VLZ-MD-22), the baseline for efficacy from the lead-in study will be used as the baseline for this study. For de novo patients, the latest nonmissing evaluation of efficacy variables (at or prior to Visit 2) before the first dose of open-label investigational product will be used as baseline. Descriptive statistics for each efficacy parameter (n, mean, SD, SEM, median, minimum, and maximum) will be presented for each visit, by cohort and by lead-in treatment group for continuous variables using observed case (OC) approach. At a specific visit, only patients in the ITT Population with both baseline and post-baseline values will be included in the summary.

In addition, by-visit analyses using the last-observation-carried-forward (LOCF) approach will be presented for each efficacy parameters. For the LOCF approach, only the postbaseline total score of a parameter will be imputed; individual item scores will not be carried forward to derive the total score. Baseline total score will be carried forward only for the intermittent missing scores immediately after baseline. If all the postbaseline values are missing, the baseline value will not be carried forward.

The efficacy parameters will include the following at selected postbaseline visits:

- Change from baseline in CDRS-R total score
- Change from baseline in Clinical Global Impressions – Severity (CGI-S) score
- Clinical Global Impressions – Improvement (CGI-I) score

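### Rollover patients with a missing Week 2 and a later assessment are given the lead-in baseline under LOCF, so their CDRS-R and CGI-S change is exactly 0 (minor; LOCF tables only)

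*SAP*

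**What the plan says.** **Baseline.** For patients who completed VLZ-MD-22, SAP 10.0 provides that "the baseline for efficacy from the lead-in study will be used as the baseline for this study"; Protocol 9.7.5 says the same. For de novo patients, SAP 10.0 uses "the latest nonmissing evaluation of efficacy variables (at or prior to Visit 2) before the first dose of open-label investigational product".

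**Imputation.** The general rule in SAP 16.2 fills a missed or out-of-window visit with the most recent observed value. The first visit has its own rule: "If the missing value occurs at Week 2, the baseline value will be carried forward for Week 2". This applies only when the patient has a later score on treatment. SAP 10.0 agrees: "Baseline total score will be carried forward only for the intermittent missing scores immediately after baseline". It also says that baseline is not carried when every postbaseline value is missing. Neither section makes a visible exception for rollover patients.

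**Presentation.** CDRS-R total score and CGI-S are summarised by visit as change from baseline. Observed cases come first in SAP 10.0, which then says: "In addition, by-visit analyses using the last-observation-carried-forward (LOCF) approach will be presented". Results are shown by cohort and by lead-in treatment group (SAP 10.0) and overall (Protocol 9.7.5).

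**The concern.** The word baseline does two jobs here. It is the reference point for change, and it is also the value carried into a missing Week 2. For de novo patients these coincide with the last available observation, so the rule is ordinary LOCF. For rollovers they separate: the reference point was recorded before the lead-in, so any lead-in or entry rating made after it is skipped.

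If rollovers improved during VLZ-MD-22, the Week 2 LOCF rows understate change from the lead-in baseline in the rollover cohort, in each lead-in treatment group and in the overall column. That earlier improvement then reappears at the next observed visit and can be read as gain under open-label treatment. The LOCF label also means different things in two cohorts that are set side by side and pooled.

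Using the lead-in baseline as the reference for change is a legitimate prespecified choice and is not disputed. The problem is only the value carried forward.

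**Working it through.** The plan states no figure to reproduce on this point. The zero follows from the rules; its effect on the tables needs assumptions.

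**1. The zero.** Let B be the lead-in baseline of a rollover patient (SAP 10.0). If Week 2 is missing or out of window and a later assessment exists, the carried Week 2 value is B (SAP 16.2). Change = B − B = 0 for every B, on both CDRS-R and CGI-S. With no later assessment, nothing is imputed. If Week 3 is missing too, SAP 10.0 carries B there as well and the change is again 0. CGI-I is not analysed as change from baseline, so it is outside this point.

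**2. A hypothetical rollover** (all scores invented): lead-in baseline 60, latest pre-dose score 35, Week 2 missing, Week 3 = 33.

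| Rule | Week 2 change | Week 3 change | Apparent step |
|---|---|---|---|
| As written | 60 − 60 = 0 | 33 − 60 = −27 | −27 |
| Latest pre-dose score carried | 35 − 60 = −25 | 33 − 60 = −27 | −2 |

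**3. Effect on the means.** Inputs, all assumed because the documents give none:

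- f, the fraction of rollovers imputed at Week 2: 3%, 5%, 10%
- d, the mean lead-in improvement in those imputed: 10, 20, 25 CDRS-R points
- r, the rollover share of patients: 30%, 50%, 70%

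The comparator is LOCF with the latest pre-dose score carried.

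| Quantity | Formula | Low | Central | High |
|---|---|---|---|---|
| Rollover row, CDRS-R | f × d | 0.03 × 10 = 0.3 | 0.05 × 20 = 1.0 | 0.10 × 25 = 2.5 |
| Overall column, CDRS-R | r × f × d | 0.3 × 0.3 = 0.09 | 0.5 × 1.0 = 0.5 | 0.7 × 2.5 = 1.75 |
| Rollover row, CGI-S (d = 1, 1.5, 2 points) | f × d | 0.03 | 0.075 | 0.20 |
| Rollover row, Week 3 CDRS-R (both visits missing in 1%, 2%, 4%) | f × d | 0.01 × 10 = 0.1 | 0.02 × 20 = 0.4 | 0.04 × 25 = 1.0 |

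**4. Patients affected** = N × r × f, treating all enrolled patients as analysed:

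- N = 315 (Protocol 9.1.2): 94.5 × 0.03 = 2.8; 157.5 × 0.05 = 7.9; 220.5 × 0.10 = 22.05
- N = 250 (SAP 14.0): 75 × 0.03 = 2.25; 125 × 0.05 = 6.25; 175 × 0.10 = 17.5

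**5. A different comparator.** Measured against the true mean Week 2 change D, assumed the same in patients with and without a Week 2 value, the LOCF mean is (1 − m) × D for missing fraction m, a shift of m × |D|. At m = 5% and D = −20 the shift is 1.0 point. Over m = 5-20% and D = −10 to −30 it runs from 0.05 × 10 = 0.5 to 0.20 × 30 = 6.0. The size depends on the inputs; the direction does not, provided rollovers are better than at their lead-in baseline.

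**The case against.** The strongest reply is that this hardly matters. The only objective is safety and tolerability, the synopsis plans no inferential analysis, and Protocol 9.7.5.1 makes no efficacy measure primary. LOCF supplements observed cases, so a reader can check the observed-case row for the same visit. No Week 2-to-Week 3 change is itself planned. All of this stands, and it is why the point is minor.

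Second, the size is entirely assumed, and the overall range spans roughly twentyfold (0.09 to 1.75). That also stands.

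Third, the point depends on text that cannot be read. The evaluation schedules and visit windows are not visible, so it cannot be confirmed that both scales are rated at Week 2 or that rollovers are rated at Visit 2. Protocol 9.3.1 treats the CDRS-R and CGI-S entry thresholds as already met for rollovers. A rollover instruction could sit in redacted text or in the separate table specifications. This limits confidence, but SAP 10.0 and 16.2 both state the rule without qualification. A score later than the lead-in baseline is a reasonable inference from completion of a controlled efficacy study (Protocol 14.0 gives its title).

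Fourth, the latest pre-dose score is not the truth either. Rollovers "will have completed a down-taper period at the end of study VLZ-MD-22" (Protocol 9.1.1), so a final lead-in rating may predate the taper and may reflect placebo or active control. That is fair, and the source of the carried score should be disclosed. It does not rescue the present rule: SAP 16.2's own general principle is to carry the most recent observed value, and the lead-in baseline is not that value wherever a later score exists.

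**Conclusion.** The concern holds. For a rollover patient with a missing or out-of-window Week 2 and at least one later assessment, the rule as written returns a CDRS-R and CGI-S change of exactly 0 regardless of the course of the lead-in. It departs from the SAP's own LOCF principle whenever a later pre-dose score exists.

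Under the stated assumptions, the rollover Week 2 LOCF mean is understated by about 1 CDRS-R point (range 0.3 to 2.5) and the overall mean by about 0.5 (range 0.09 to 1.75). About 8 patients would be affected if 315 enrol (range 3 to 22), or about 6 if 250 enrol (range 2 to 18). The direction assumes that rollovers improved in the lead-in.

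The rule should be corrected, but it is a minor matter confined to descriptive LOCF tables. Confidence is medium because the schedules and possibly relevant text are redacted.

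**What to change.** Add to SAP 10.0 and 16.2, for example: *If a rollover patient has no Week 2 value but has at least one later assessment, the most recent score available ahead of the first open-label dose is carried into Week 2; change continues to be computed from the lead-in baseline. If no score later than the lead-in baseline is available, Week 2 stays missing.* Apply the same source to directly consecutive missing visits, and footnote the LOCF tables to show where the carried score came from (entry to this study or the final lead-in rating).

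The cost is one SAP sentence and one footnote. It needs no new assessments, because it uses scores already held from this study or the lead-in and has a fallback where none exists. There are two downsides. A final lead-in score may predate the down-taper and reflect another treatment, so it too is an assumption. Leaving Week 2 missing where no later score exists slightly reduces n at that visit. De novo rules, observed-case tables and the choice of baseline are unchanged.

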16.3 AGE-AND-GENDER_CORRELATED VALUES FOR WEIGHT AND HEIGHT

To adjust weight (kg) and height (cm) for sex and age, one needs to compare them to standard reference values for the same sex and age group, which are available in the United States Growth Charts and can be downloaded from:

http://www.cdc.gov/growthcharts/percentile_data_files.htm

The z-score is calculated as below

$$z = \frac{(X / M)^L - 1}{SL}, \text{ if } L \neq 0 \text{ and}$$

$$z = \frac{\ln(X / M)}{S}, \text{ if } L = 0,$$

where X is the physical measurement (eg weight and height) and L, M, and S are the values from the appropriate table corresponding to the age in months (or length/stature) and sex (1 = male; 2 = female). X must be in metric measurements (kilograms or meters). This is called LMS method (Cole TJ, 1990), and parameters L, M, and S are the Box-Cox transformation power, median, and SD, respectively, in the reference data, which are provided in the reference data tables.

16.4 REPEATED OR UNSCHEDULED ASSESSMENTS OF SAFETY PARAMETERS

For roll-over patients, the corresponding baseline of the double-blind lead-in study will be used. If a de novo patient has repeated assessments before the date of the first dose of open-label investigational product, the results from the final nonmissing assessment made before the date of the first dose of open-label investigational product will be used as baseline. If the end-of-open-label-treatment period assessments are repeated or if unscheduled visits occur, the last nonmissing postbaseline assessment during the open-label treatment period will be used as the end-of-open-label-treatment-period assessment for generating summary statistics. Likewise, if the end of open-label down-taper period assessments are repeated or if unscheduled visits occur, the last non-missing assessment during the open-label down-taper period will be used as the end-of-open-label-down-taper-period assessment for generating summary statistics. However, all postbaseline assessments will be used to determine PCS values for laboratory parameters, vital signs and ECG parameters, and to determine most severe suicidal ideation and most severe suicidal behavior from C-SSRS. All assessments will be presented in the data listings.

16.5 MISSING DATE OF INVESTIGATIONAL PRODUCT

[figure not shown]
When the date of the last dose of the open-label investigational product during the study treatment period is missing for a patient in the Safety Population, all efforts should be made to obtain the date from the Investigator. If it is still missing after all efforts have been made, then the last available dosing record date will be used as the last dose date.

[figure not shown]
**16.6 MISSING SEVERITY TO INVESTIGATIONAL PRODUCT IN
ADVERSE EVENTS**

[figure not shown]
If the severity is missing for an AE started on or after the date of the first dose of the open-label investigational product, then a severity of “Severe” will be assigned. The imputed values for severity assessment will be used for incidence summary, while the actual values should be presented in data listings.

[figure not shown]
**16.7 MISSING RELATIONSHIP TO INVESTIGATIONAL
PRODUCT FOR ADVERSE EVENTS**

If the relationship to the investigational product is missing for an AE started on or after the date of the first dose of the open-label investigational product, a causality of “Related” will be assigned. The imputed values for relationship to the investigational product will be used for incidence summary, while the actual values should be presented in data listings.

16.10**CHARACTER VALUES OF CLINICAL LABORATORY
PARAMETERS**

If the reported value of a clinical laboratory parameter cannot be used in a statistical summary table due, for example, to the fact that a character value is reported for a parameter of the numerical type, a coded value needs to be appropriately determined and used in the statistical analyses. However, the actual values as reported in the database will be presented in data listings.

17.0**CHANGES TO ANALYSES SPECIFIED IN PROTOCOL**

No major changes have been made to the original protocol dated 15 Dec 2014.

18.0**REFERENCES**

Cole TJ. The LMS method for constructing normalized growth standards. *Eur J Clin Nutr*. 1990, 44: 45-60.

19.0

APPENDICES

APPENDIX I. REPORTING SELECTED LABORATORY PARAMETERS IN CONVENTIONAL UNIT

All clinical laboratory parameters will be reported in the International System (SI) units as standard practice. In addition, descriptive statistics for values and changes from baseline in conventional units at all assessed visits will be reported for selected laboratory parameters
